#### 9.4.3 Other analyses

Pharmacokinetic exploratory analyses will be described in the statistical analysis plan finalized before database lock. Analyses of other endpoints are detailed in [Table 7](#).

**Table 7 - Other analyses**

Endpoint	Statistical Analysis Methods
Efpeglenatide ADA	
Summaries of ADA data will be for participants treated with efpeglenatide only. All summaries related to kinetics of ADA response (ADA status and magnitude, ADA attributes, participant status, ADA incidence) will be descriptive; no statistical significance tests will be performed on ADA data:
 
 
Number and percentage of participants by ADA status (positive/negative) at scheduled visits
 
Number and percentage of participants with treatment-induced ADAs (among the participants with ADA negative or missing at baseline) during the study period
 
Number and percentage of participants with treatment-boosted ADAs (among the participants with ADA positive at baseline) during the study period
 
ADA titer at schedule timepoint will be summarized by visit using descriptive statistics by number (n), median, quartiles, minimum, and maximum.
 
Number and percentage of participants by ADA cross-reactivity to endogenous GLP-1 (positive or
 

Endpoint	Statistical Analysis Methods
	
negative) at scheduled visits
 

Number and percentage of participants by ADA cross-reactivity to endogenous glucagon (positive or negative) at scheduled visits

Number and percentage of participants with ADAs directed against the PEG linker of efpeglenatide at scheduled visits.

 
Correlation, scatterplots and/or subgroup analyses will be conducted as appropriate to assess the relationship between immunogenicity endpoints and efficacy/safety assessments.

PK endpoints: serum concentration of efpeglenatide at pre-dose and post-dose	Efpeglenatide pre-dose and post-dose serum concentrations of participants in the efpeglenatide groups will be listed and summarized by visit in the PK population, using descriptive statistics by N, geometric mean, coefficient of variation, median, minimum and maximum.
PRO:	
The analysis of PRO endpoints will be descriptive with no formal testing. Summary statistics at scheduled visits will be provided by treatment group. Graphical presentations will also be used to illustrate trends over time.
 
Participants' answers to the open-ended questions of PQATv2 will be analyzed qualitatively and quantitatively, as relevant, using appropriate data analysis software.
 
The analysis method for this exploratory analysis will be provided in a separate SAP and the analyses results will be documented in a separate report.

ADA anti-drug antibodies; GLP-1 glucagon-like peptide 1; PEG polyethylene glycol, PK pharmacokinetic; PQATv2 Patient Qualitative Assessment of Treatment version 2; PRO participant-reported outcome ; SAP statistical analysis plan.

## 9.5 INTERIM ANALYSES

Not applicable.

### 9.5.1 Data Monitoring Committee

See Appendix 1 ([Section 10.1](#)) for details.

## 10 SUPPORTING DOCUMENTATION AND OPERATIONAL CONSIDERATIONS

### 10.1 APPENDIX 1: REGULATORY, ETHICAL, AND STUDY OVERSIGHT CONSIDERATIONS

#### 10.1.1 Regulatory and Ethical Considerations

- This study will be conducted in accordance with the protocol and with the following:
  - Consensus ethical principles derived from international guidelines including the Declaration of Helsinki and Council for International Organizations of Medical Sciences (CIOMS) International Ethical Guidelines
  - Applicable International Council for Harmonisation (ICH) Good Clinical Practice (GCP) Guidelines
  - Applicable laws and regulations
- The protocol, protocol amendments, ICF, IB, and other relevant documents (eg, advertisements) must be submitted to an IRB/IEC by the Investigator and reviewed and approved by the IRB/IEC before the study is initiated.
- Any amendments to the protocol will require IRB/IEC approval before implementation of changes made to the study design, except for changes necessary to eliminate an immediate hazard to study participants.
- The Investigator will be responsible for the following:
  - Providing written summaries of the status of the study to the IRB/IEC annually or more frequently in accordance with the requirements, policies, and procedures established by the IRB/IEC
  - Notifying the IRB/IEC of SAEs or other significant safety findings as required by IRB/IEC procedures
  - Providing oversight of the conduct of the study at the site and adherence to requirements of 21 CFR, ICH guidelines, the IRB/IEC, European regulation 536/2014 for clinical studies (if applicable), and all other applicable local regulations

#### 10.1.2 Informed Consent Process

- The Investigator or his/her representative will explain the nature of the study to the participant and answer all questions regarding the study.
- Participants must be informed that their participation is voluntary. Participants will be required to sign a statement of informed consent that meets the requirements of 21 CFR 50, local regulations, ICH guidelines, Health Insurance Portability and Accountability Act requirements, where applicable, and the IRB/IEC or study center.

- The medical record must include a statement that written informed consent was obtained before the participant was enrolled in the study and the date the written consent was obtained. The authorized person obtaining the informed consent must also sign the ICF.
- Participants must be re-consented to the most current version of the ICF(s) during their participation in the study.
- A copy of the ICF(s) must be provided to the participant.
- Participants who are rescreened are required to sign a new ICF.
- The ICF will contain a separate section that addresses the participation in the post-dose PK assessment sub-study. The Investigator or authorized designee will explain to each participant the objectives of the exploratory research. Participants will be told that they are free to refuse to participate and may withdraw their consent at any time and for any reason during the storage period. A separate signature will be required to document a participant's agreement to allow any remaining specimens to be used for exploratory research. Participants who decline to participate in this optional research will not provide this separate signature.

#### **10.1.3 Data Protection**

- Participants will be assigned a unique identifier by the Sponsor. Any participant records or datasets that are transferred to the Sponsor will contain the identifier only; participant names or any information which would make the participant identifiable will not be transferred.
- The participant must be informed that his/her personal study-related data will be used by the Sponsor in accordance with local data protection law. The level of disclosure must also be explained to the participant.
- The participant must be informed that his/her medical records may be examined by Clinical Quality Assurance auditors or other authorized personnel appointed by the Sponsor, by appropriate IRB/IEC members, and by inspectors from regulatory authorities.
- Participants' race and ethnicity (race: Asian, Black or African American, White, Other not reported, unknown; ethnicity: Hispanic, Not Hispanic) will be collected in this study because these data are required by several regulatory authorities (eg, on African American population for US FDA).
- The data collected in this study will only be used for the purpose(s) of the study and to document the evaluation of the benefit/risk ratio, efficacy, and safety of the product(s). They may be further processed if they have been anonymized.

## **10.1.4 Committees Structure**

### **10.1.4.1 Data Monitoring Committee**

An independent DMC with members who are independent from the Sponsor and the Investigators will meet on a regular basis and will be responsible for:

- Review of accumulating clinical study safety data, and
- Making a recommendation to the Sponsor regarding the study following each meeting

The DMC reviews and analyzes, on a regular basis, unblinded safety data throughout the study, as well as safety data from the other ongoing clinical studies conducted with efpeglenatide (a single DMC for the whole efpeglenatide program). Details describing the DMC processes and procedures are outlined in the DMC Charter. To maintain continuous blinding and study integrity, the analysis will be conducted by an independent statistician who will directly transfer data to DMC members, and measures will be taken to ensure the validity of the data.

### **10.1.4.2 Clinical Endpoint Committee**

Independent CEC(s) will be composed of experts in the field of cardiology, neurology and gastroenterology (and other appropriate medical specialties as needed). This committee will be independent from the Sponsor, the CRO and the Investigators, and will be implemented to review, assess and/or adjudicate all events of death, selected cardiovascular events (non-fatal myocardial infarction, stroke, unstable angina leading to hospitalization, and heart failure leading to hospitalization), pancreatic events and other selected AEs (to be defined in the CEC charter). This review will be conducted in a blinded manner with regard to study treatment.

### **10.1.4.3 Independent Expert**

An independent ophthalmologist expert will review in a treatment-blinded manner all reported AEs suspected to be diabetic retinopathy-related to assess the presence of retinopathy and relationship of reported AE to IMP.

Investigators are reminded that all patients should have eye examinations based on their retinopathy status, performed by a professional eye care provider according to ICO guidelines (10) or local standards. Especially for patients at high risk this should occur at minimum quarterly.

## **10.1.5 Dissemination of Clinical Study Data**

Sanofi shares information about clinical trials and results on publically accessible websites, based on company commitments, international and local legal and regulatory requirements, and other clinical trial disclosure commitments established by pharmaceutical industry associations. These websites include clinicaltrials.gov, European Union clinicaltrialregister (eu.ctr), and sanofi.com, as well as some national registries.

In addition, results from clinical trials in participants are required to be submitted to peer reviewed journals following internal company review for accuracy, fair balance and intellectual property. For those journals that request sharing of the analyzable data sets that are reported in the publication, interested researchers are directed to submit their request to [clinicalstudydatarequest.com](http://clinicalstudydatarequest.com).

Individual participant data and supporting clinical documents are available for request at [clinicalstudydatarequest.com](http://clinicalstudydatarequest.com). While making information available we continue to protect the privacy of participants in our clinical trials. Details on data sharing criteria and process for requesting access can be found at this web address: [clinicalstudydatarequest.com](http://clinicalstudydatarequest.com).

#### **10.1.6 Data Quality Assurance**

- All participant data relating to the study will be recorded on printed or e-CRF unless transmitted to the Sponsor or designee electronically (eg, laboratory data). The Investigator is responsible for verifying that data entries are accurate and correct by physically or electronically signing the CRF.
- The Investigator must maintain accurate documentation (source data) that supports the information entered in the CRF.
- The Investigator must permit study-related monitoring, audits, IRB/IEC review, and regulatory agency inspections and provide direct access to source data documents.
- The Sponsor or designee is responsible for the data management of this study including quality checking of the data.
- Study monitors will perform ongoing source data verification to confirm that data entered into the CRF by authorized site personnel are accurate, complete, and verifiable from source documents; that the safety and rights of participants are being protected; and that the study is being conducted in accordance with the currently approved protocol and any other study agreements, ICH GCP, and all applicable regulatory requirements.
- Records and documents, including signed ICFs, pertaining to the conduct of this study must be retained by the Investigator for 15 years after study completion unless local regulations or institutional policies require a longer retention period. No records may be destroyed during the retention period without the written approval of the Sponsor. No records may be transferred to another location or party without written notification to the Sponsor.

#### **10.1.7 Source documents**

- Source documents provide evidence for the existence of the participant and substantiate the integrity of the data collected. Source documents are filed at the Investigator's site.
- Data reported on the CRF or entered in the e-CRF that are transcribed from source documents must be consistent with the source documents or the discrepancies must be explained. The Investigator may need to request previous medical records or transfer records, depending on the study. Also, current medical records must be available.
- Definition of what constitutes source data can be found in a separate study document.

### **10.1.8 Study and Site Closure**

The Sponsor or designee reserves the right to close the study site or terminate the study at any time for any reason at the sole discretion of the Sponsor. Study sites will be closed upon study completion. A study site is considered closed when all required documents and study supplies have been collected and a study-site closure visit has been performed.

The Investigator may initiate study-site closure at any time, provided there is reasonable cause and sufficient notice is given in advance of the intended termination.

Reasons for the early closure of a study site by the Sponsor or Investigator may include but are not limited to:

- Failure of the Investigator to comply with the protocol, the requirements of the IRB/IEC or local health authorities, the Sponsor's procedures, or GCP guidelines
- Inadequate recruitment of participants by the Investigator
- Discontinuation of further study intervention development

### **10.1.9 Publication Policy**

- The results of this study may be published or presented at scientific meetings. If this is foreseen, the Investigator agrees to submit all manuscripts or abstracts to the Sponsor before submission. This allows the Sponsor to protect proprietary information and to provide comments.
- The Sponsor will comply with the requirements for publication of study results. In accordance with standard editorial and ethical practice, the Sponsor will generally support publication of multicenter studies only in their entirety and not as individual site data. In this case, a coordinating Investigator will be designated by mutual agreement.
- Authorship will be determined by mutual agreement and in line with International Committee of Medical Journal Editors authorship requirements.

## **10.2 APPENDIX 2: CLINICAL LABORATORY TESTS**

- The tests detailed in [Table 8](#) will be performed by the central laboratory, except urine pregnancy tests and urinalysis by dipstick, which will be performed locally.
- Protocol-specific requirements for inclusion or exclusion of participants are detailed in [Section 5](#) of the protocol.
- Additional tests may be performed at a local laboratory at any time during the study as determined necessary by the Investigator or required by local regulations. If they are used to evaluate an AE (diagnostic, follow-up, outcome), the results must be entered into the e-CRF.

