#### **8.2.4 Clinical safety laboratory assessments**

See Appendix 2 ([Section 10.2](#)) for the list of clinical laboratory tests to be performed and to the SoA ([Section 1.3](#)) for the timing and frequency of sample collection.

- The Investigator must review the laboratory report, document this review, and record any clinically relevant changes occurring during the study in the AE section of the e-CRF. The laboratory reports must be filed with the source documents. Clinically significant abnormal laboratory findings are those which are not associated with the underlying disease, unless judged by the Investigator to be more severe than expected for the participant's condition.
- All laboratory tests with values considered clinically significantly abnormal during participation in the study should be repeated until the values return to normal or Baseline or are no longer considered clinically significant by the Investigator or Medical Monitor.
  - If such values do not return to normal or Baseline within a period of time judged reasonable by the Investigator, the etiology should be identified and the Sponsor notified.
- All protocol-required laboratory assessments, as defined in Appendix 2 ([Section 10.2](#)), must be conducted in accordance with the laboratory manual and the SoA ([Section 1.3](#)).
- If local laboratory results are used to make study treatment decision, for response evaluation, or to diagnose/follow-up and AEs, then the results must be recorded in the e-CRF.
- Recommended decision trees for the management of certain laboratory abnormalities are provided in Appendix 5 ([Section 10.5.1](#)).

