2.4.5.5 Analyses of laboratory variables

All hematology and clinical chemistry results will be listed by treatment group, participants and visit, including scheduled and unscheduled/repeat measurements.

The summary statistics (including number, mean, median, standard deviation, minimum and maximum) of all protocol-required laboratory variables (central laboratory values and changes from Baseline) will be calculated for each scheduled visit and last value on treatment by treatment group.

The incidence of PCSAs at any time during the whole on-treatment period will be summarized by biological function and treatment group whatever the Baseline level and/or according to the following Baseline status categories:

- Normal/missing
- Abnormal according to PCSA criterion or criteria

For parameters for which no PCSA criteria are defined, similar table(s) using the normal range will be provided. For calcitonin, no PCSA criterion is defined. Similar summaries will be provided using the pre-defined categories: \leq ULN, $>$ ULN - $<$ 20 ng/L, \geq 20 - $<$ 50 ng/L, and \geq 50 ng/L (Note that ng/L is the standard international unit and is equivalent to pg/mL).

All measurements collected during the whole on-treatment period, including values from unscheduled visits, will be considered for the PCSA summaries. These summaries will include participants in the safety population who have at least 1 assessment performed during the whole on-treatment period. When a PCSA definition involves only a change from baseline value, participants must also have a baseline value to be included in the summaries, and when required by the definition of the abnormality, participants must also have available laboratory normal ranges.

For some parameters, such as liver enzymes, the lower limit of normal (LLN) is not considered clinically relevant, and values below this limit are considered normal. When there are multiple PCSA criteria for a specific parameter (eg, ALT), the participant will be counted once during the whole on-treatment period for the specific parameter in question under the worst/maximum PCSA category.

Elevated liver parameters will be summarized by treatment group in safety population.

For PCSA, both central and local lab data will be used.

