Missing or partial AE/hypoglycemia onset dates and times will be imputed so that if the partial AE/hypoglycemia onset date/time information does not indicate that the AE/hypoglycemia started prior to treatment or after the whole on-treatment period, the AE/hypoglycemia will be classified as treatment-emergent. No imputation of AE end dates/times will be performed. These data

imputations are for categorization purpose only and will not be used in listings. No imputation is planned for date/time of AE resolution.

Handling of adverse events/hypoglycemia when date and time of first investigational medicinal product administration is missing

When the date and time of the first IMP administration is missing, all AEs/hypoglycemia that occurred on or after the day of randomization should be considered as TEAEs. The exposure duration should be kept as missing.

Handling of missing assessment of relationship of adverse events to investigational medicinal product

If the assessment of the relationship to IMP is missing, then the relationship to IMP has to be assumed and the AE considered as such in the frequency tables of possibly related AEs, but no imputation should be done at the data level.

Handling of missing intensity of adverse events

If the intensity is missing for 1 of the treatment-emergent occurrences of an AE, the maximal intensity on the remaining occurrences will be considered. If the intensity is missing for all the occurrences, a “missing” category will be added in the summary table.

Handling of potentially clinically significant abnormalities

If a participant has a missing Baseline, he or she will be grouped in the category “normal/missing at Baseline.”

For PCSAs with 2 conditions, one based on a change from Baseline value or a normal range and the other on a threshold value, with the first condition being missing, the PCSA will be based only on the second condition.

For a PCSA defined on a threshold and/or a normal range, this PCSA will be derived using this threshold if the normal range is missing; eg, for eosinophils the PCSA is >0.5 GIGA/L or $>ULN$ if $ULN \geq 0.5$ GIGA/L. When ULN is missing, the value 0.5 should be used.

Measurements flagged as invalid by the laboratory will not be summarized or taken into account in the computation of PCSA values.

Handling of missing screening value to derive actual randomization strata

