2.5.4 Windows for time points

Nominal post-baseline visits will be used for descriptive statistics and time course plots.

Display of safety data by visit (laboratory variables and vital signs)

Descriptive statistics (N, mean, SD, minimum, median, maximum) of quantitative laboratory variables and vital signs (observed data and change from baseline) during the whole on-treatment period for all scheduled visits as per protocol will be provided (ie, only including participants having non-missing assessments at a nominal visit). Summaries showing data by visit will be presented according to the visit number and labeled with the targeted approximate day/week.

As specified in the study protocol, laboratory data from scheduled visits are reported by central laboratories. When both central and local laboratories report values from the same blood sample (ie, sample collected at the same date and time), only measurements from the central laboratory will be included in the analyses. When only local laboratory results are reported, and central laboratory results are unavailable, the local results will not be used in the efficacy analyses. In the safety analyses, local results will only be used in the PCSA summary if they are accompanied by a local laboratory normal range.

When a participant has more than 1 measurement from the central laboratory for the same laboratory parameter on the same date, the average of the measurements will be used. For the same laboratory parameter, if a participant has more than one measurement on different dates for the same scheduled visit, the value closest to the scheduled visit will be used for the scheduled visit. When the values for the same scheduled visit are equidistant, the last value should be used for the scheduled visit.

Efficacy data at Week 30/Week 56

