CPK	>3 ULN >10 ULN	FDA Feb 2005. Am J Cardiol April 2006. Categories are cumulative. First row is mandatory. Rows following one mentioning zero can be deleted.
CLcr (mL/min) (Estimated creatinine clearance based on the Cokcroft-Gault equation)	<15 (end stage renal disease) ≥15 - <30 (severe decrease in GFR) ≥30 - < 60 (moderate decrease in GFR) ≥60 - <90 (mild decrease in GFR) ≥ 90 (normal GFR)	FDA draft Guidance 2010 Pharmacokinetics in patients with impaired renal function-study design, data analysis, and impact on dosing and labeling
eGFR (mL/min/1.73m2) (Estimate of GFR based on an MDRD equation)	<15 (end stage renal disease) ≥15 - <30 (severe decrease in GFR) ≥30 - < 60 (moderate decrease in GFR) ≥60 - <90 (mild decrease in GFR) ≥ 90 (normal GFR)	FDA draft Guidance 2010 Pharmacokinetics in patients with impaired renal function-study design, data analysis, and impact on dosing and labeling
Creatinine	≥150 µmol/L (Adults) ≥30% change from baseline ≥100% change from baseline	Benichou C., 1994.
Uric Acid		Harrison- Principles of internal Medicine 17 th Ed., 2008.
Hyperuricemia	>408 µmol/L	
Hypouricemia	<120 µmol/L	
Blood Urea Nitrogen	≥17 mmol/L	
Chloride	<80 mmol/L ≥115 mmol/L	
Sodium	≤129 mmol/L ≥160 mmol/L	
Potassium	<3 mmol/L ≥5.5 mmol/L	FDA Feb 2005.
Total Cholesterol	≥7.74 mmol/L	Threshold for therapeutic intervention.
Triglycerides	≥4.6 mmol/L	Threshold for therapeutic intervention.
Lipasemia	≥3 ULN	
Amylasemia	≥3 ULN	
Glucose		
Hypoglycaemia	≤3.9 mmol/L and <LLN	ADA May 2005.
Hyperglycaemia	≥11.1 mmol/L (unfasted); ≥7 mmol/L (fasted)	ADA Jan 2008.

Parameter	PCSA	Comments
HbA1c	>8%	
Albumin	≤25 g/L	
CRP	>2 ULN or >10 mg/L (if ULN not provided)	FDA Sept 2005.
Hematology		
WBC	<3.0 Giga/L (Non-Black); <2.0 Giga/L (Black) ≥16.0 Giga/L	Increase in WBC: not relevant. To be interpreted only if no differential count available.
Lymphocytes	>4.0 Giga/L	
Neutrophils	<1.5 Giga/L (Non-Black); <1.0 Giga/L (Black)	International Consensus meeting on drug-induced blood cytopenias, 1991. FDA criteria.
Monocytes	>0.7 Giga/L	
Basophils	>0.1 Giga/L	
Eosinophils	>0.5 Giga/L or >ULN (if ULN ≥0.5 Giga/L)	Harrison- Principles of internal Medicine 17 th Ed., 2008.
Hemoglobin	≤115 g/L (Male); ≤95 g/L (Female) ≥185 g/L (Male); ≥165 g/L (Female) Decrease from Baseline ≥20 g/L	Criteria based upon decrease from baseline are more relevant than based on absolute value. Other categories for decrease from baseline can be used (≥30 g/L, ≥40 g/L, ≥50 g/L).

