Hematocrit	≤0.37 v/v (Male); ≤0.32 v/v (Female) ≥0.55 v/v (Male); ≥0.5 v/v (Female)	
RBC	≥6 Tera/L	Unless specifically required for particular drug development, the analysis is redundant with that of Hb. Otherwise, consider FDA criteria.
Platelets	<100 Giga/L ≥700 Giga/L	International Consensus meeting on drug-induced blood cytopenias, 1991.
Urinalysis		
pH	≤4.6 ≥8	
Vital signs		
HR	≤50 bpm and decrease from baseline ≥20 bpm ≥120 bpm and increase from baseline ≥20 bpm	To be applied for all positions (including missing) except STANDING.

Parameter	PCSA	Comments
SBP	≤ 95 mmHg and decrease from baseline ≥ 20 mmHg ≥ 160 mmHg and increase from baseline ≥ 20 mmHg	To be applied for all positions (including missing) except STANDING.
DBP	≤ 45 mmHg and decrease from baseline ≥ 10 mmHg ≥ 110 mmHg and increase from baseline ≥ 10 mmHg	To be applied for all positions (including missing) except STANDING.
Orthostatic Hypotension		
Orthostatic SDB	≤ -20 mmHg	
Orthostatic DBP	≤ -10 mmHg	
Weight	$\geq 5\%$ increase from baseline $\geq 5\%$ decrease from baseline	FDA Feb 2007.
ECG		Ref.: ICH E14 guidance (2005) and E14 Q&A (2012), and Cardiac Safety Research Consortium White Paper on PR and QRS (Nada et al. Am Heart J. 2013; 165(4): 489-500)
HR	<50 bpm <50 bpm and decrease from baseline ≥ 20 bpm <40 bpm <40 bpm and decrease from baseline ≥ 20 bpm <30 bpm <30 bpm and decrease from baseline ≥ 20 bpm >90 bpm >90 bpm and increase from baseline ≥ 20 bpm >100 bpm >100 bpm and increase from baseline ≥ 20 bpm >120 bpm >120 bpm and increase from baseline ≥ 20 bpm	Categories are cumulative

Parameter	PCSA	Comments
PR	
>200 ms
 
>200 ms and increase from baseline ≥25%
 
> 220 ms
 
>220 ms and increase from baseline ≥25%
 
> 240 ms
 
> 240 ms and increase from baseline ≥25%
	Categories are cumulative
QRS	
>110 ms
 
>110 msec and increase from baseline ≥25%
 
>120 ms
 
>120 ms and increase from baseline ≥25%
	Categories are cumulative
QT	>500 ms	
QTc	
Absolute values (ms)
 
>450 ms
 
>480 ms
 
>500 ms
 
Increase from baseline
 
Increase from baseline]30-60] ms
 
Increase from baseline >60 ms
	
To be applied to any kind of QT correction formula.
 
Absolute values categories are cumulative
 
QTc >480 ms and QTc>60 ms are the 2 PCSA categories to be identified in individual subjects/patients listings.

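### SAP 2.5.4 requires a local normal range before any local laboratory result counts as a PCSA, which conflicts with SAP 2.4.5.5 and is unnecessary for most Appendix B criteria

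*Protocol*

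**What the plan says.** Protocol Appendix 2 (Section 10.2) lets sites run extra tests locally and adds: "If they are used to evaluate an AE (diagnostic, follow-up, outcome), the results must be entered into the e-CRF". Protocol Section 8.2.4 sets a similar duty for local results behind a treatment decision, a response evaluation or an AE: "then the results must be recorded in the e-CRF". Neither place mentions entering the local normal range with the value.

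Three parts of the SAP bear on what happens to such a value in the PCSA tables:

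- SAP 2.4.5.5 states without qualification: "For PCSA, both central and local lab data will be used". On ranges, it says that "when required by the definition of the abnormality, participants must also have available laboratory normal ranges". It also brings values from unscheduled visits into the PCSA summaries.
- SAP 2.5.3 covers criteria built on a threshold and/or a normal range: "this PCSA will be derived using this threshold if the normal range is missing". Eosinophils are its example.
- SAP 2.5.4 states that "local results will only be used in the PCSA summary if they are accompanied by a local laboratory normal range". It makes no exception by type of criterion.

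The SAP gives no order of precedence among these rules.

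**The concern.** A normal range is needed to classify a value only when the criterion refers to one. Many Appendix B criteria are absolute cut-offs or changes from baseline. The platelet row, for example, reads "<100 Giga/L ≥700 Giga/L". Under SAP 2.5.4 a local platelet count without a range is left out even though its criterion makes no use of a range. Under SAP 2.4.5.5 the same value is counted. Two programmers working from the same data could produce different tables.

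The completeness of the abnormality counts is at stake. Local samples tend to be taken between scheduled visits. The Schedule of Activities is broken in the copy reviewed, but as best it can be read, chemistry and hematology after Week 12 fall at Weeks 30, 43 and 56, that is 18, 13 and 13 weeks apart (30−12, 43−30, 56−43). A transient abnormality could exist only as a local value.

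**Working it through.** This is a comparison of texts plus a count. The plan states no figure on this point to reproduce.

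**1. Follow one value through the rules.** Take a hypothetical local platelet count of 80 Giga/L, entered for an AE without a range.

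- SAP 2.4.5.5: local data are used, the definition needs no range, and 80 < 100. The value counts.
- SAP 2.5.3: this addresses criteria that may involve a range and prefers the threshold when the range is absent. It does not mention local data, but its logic also favors counting.
- SAP 2.5.4: there is no local range, so the value is not used in the PCSA summary.

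**2. Count the parameters affected.** The inputs are protocol Table 8 and SAP Appendix B.

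- Blood parameters in the hematology, chemistry, lipid and calcitonin rows of Table 8: 10 + 10 + 4 + 1 = 25.
- No Appendix B criterion: LDL cholesterol, HDL cholesterol and calcitonin (3). With a criterion: 25 − 3 = 22.
- Criterion needs the ULN: ALT, AST, alkaline phosphatase, total bilirubin, amylase and lipase (6).
- Fixed threshold that works when the ULN is missing (SAP 2.5.3): eosinophils (1).
- No range needed: creatinine, eGFR, sodium, potassium, total cholesterol, triglycerides, WBC, lymphocytes, neutrophils, monocytes, basophils, hemoglobin, hematocrit, RBC and platelets (15).
- Check: 6 + 1 + 15 = 22.
- Share for which the range is not needed: 15/22 = 68%, or 16/22 = 73% with eosinophils.

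**3. What the count does not measure.** It counts parameters, not participants or results. The documents give neither the number of local results nor the share without a range, which could be anything from 0% to 100%. With about 100 participants per arm, one participant left out changes an incidence by 1/100 = 1 percentage point.

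**4. Conditions for a loss.** All of these must hold:

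- the value is local;
- no local range was recorded with it;
- its criterion needs no range;
- SAP 2.5.4 is the rule programmed;
- no other counted value for that participant in the same period meets the criterion.

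**The case against.** The best defense is that the rules can be applied in sequence. SAP 2.5.4 is the only one written specifically for local results, so it decides which local values enter. SAP 2.4.5.5 and 2.5.3 then govern classification. On this view the general statement about central and local data is met once local values with a range are used. The sentence on ranges in 2.4.5.5 concerns which participants are included, and 2.5.3 still serves central values. Demanding a range is also a defensible quality rule when values come from many laboratories with different units.

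This reading has force, but it does not remove the problem. No precedence is stated. If 2.5.4 does prevail, the plan still drops values whose classification needs no range. Doubt about units calls for a unit check rather than exclusion. For the six ULN-based parameters the range condition is justified.

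Other outputs limit the damage. A local result entered to evaluate an AE should have an AE record behind it, and treatment-emergent AEs are tabulated. SAP 2.4.5.5 lists all hematology and chemistry results, including unscheduled ones. Protocol 10.5.4 directs creatinine to the central laboratory, if clinically indicated, in prolonged or severe nausea and vomiting. Protocol 10.5.2.1 asks for amylase and lipase retests to be central as far as possible. These are partial substitutes. A listing gives no incidence, protocol 10.5.1 makes neutropenia, thrombocytopenia and raised creatinine AEs only if general criteria are met, and neither central-testing instruction covers sodium, potassium or hematology.

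A reader might infer more than the documents support:

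- *That abnormalities found during acute illness go uncounted.* Nothing says local ranges are not collected, the e-CRF is not among the documents, and all the conditions listed above must hold.
- *That the loss falls mainly on the active arms.* The protocol describes nausea and vomiting as dose-related, but gives no rate of missing ranges by arm, and it sends creatinine in such episodes to the central laboratory.
- *That the urinalysis pH criterion can never be counted.* Dipstick testing is local, but whether a range accompanies it is unknown. Appendix B is also a general list with rows for tests this trial does not require, such as uric acid and CRP, so a row there does not prove a planned table.

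**Conclusion.** The point holds as a conflict within the SAP and, if 2.5.4 governs, as an exclusion without a reason for 15 of 22 parameters (16 with eosinophils). A valid local abnormality recorded without a range could be missing from the PCSA counts. The effect on incidence cannot be computed from the documents and may be nil. It is confined to descriptive safety tables; no efficacy analysis or hypothesis test is touched. The conclusion assumes that Appendix B applies to the Table 8 parameters as written and that at least some local values arrive without a range. It is still worth correcting before the tables are programmed, because the change is small and removes a choice that would otherwise be left to the programmer.

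**What to change.** Replace the sentence on local results in SAP 2.5.4 with text along these lines: *Local results are used in the PCSA summary. A local normal range is required only where the criterion or table uses the ULN, the LLN or the normal range. For absolute-threshold and change-from-baseline criteria, the local value is used after verification of its unit, even if the range is missing, consistent with Sections 2.4.5.5 and 2.5.3.*

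The wording should name the LLN and the normal range as well as the ULN. Appendix B has a glucose criterion that uses the LLN, and SAP 2.4.5.5 bases tables on the normal range for parameters without a PCSA criterion. The existing rule that a central value takes priority when both laboratories report the same sample can stay.

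The cost is one SAP sentence, one programming condition and a unit check on local values that lack a range.
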